## **5. Study design and Methods**

**Overview:** To accomplish Aim 1, we will use functional Magnetic Resonance Imaging (fMRI) to determine neural circuitry underlying IG and EG foot-tapping in 24 veterans with and 24 veterans without idiopathic, mild-moderate PD (Hoehn & Yahr stages II-III). To accomplish Aim 2, we propose a randomized controlled trial to evaluate the relative effectiveness of IG and EG movement to improve mobility in veterans with PD. We will also measure corresponding changes in neural activation during IG and EG foot-tapping, as a result of intervention. Participants will be randomized

to receive EG, IG or behavioral control (BC; health education) training over 12 weeks. Participants will be tested on all outcome measures while “OFF” and “ON” medications at a standardized time of day. We are observing participants in outcome measures while OFF medications in order to avoid dyskinesia, and medication fluctuations that may impact functional activity of networks of interest. Participants will complete outcome measure testing for mobility, QOL, executive function, procedural learning, spatial cognition, and foot-tapping 1 week before training (pre), and 1 week (post) and one month (follow-up) after completing all training. Using fMRI we will also investigate the relationship of changes in neural activation in the participants before and immediately after training.

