The instructor and healthy assistants, trained in spotting techniques, shall carefully monitor all participants' safety. Participants will be encouraged to take regular breaks. Spouses, friends and caregivers will serve as dance partners. Also with methods used several times previously by the PI, student volunteers recruited from surrounding colleges and universities will serve as assistants and dance partners. The PI will educate student volunteers about PD- and aging-related posture and gait problems, proper assistance techniques to use for balance loss and methods for monitoring balance and anticipating falls.

**Behavioral Control (BC) Condition:** Participants will attend group health education sessions as per Wolf et al., (1996) adapted to the needs and interests of individuals with PD. They will engage in *IRB 60613 Motor Training in PD*

Study Version 6/14/16

interactive small group, large group and partnered learning. Discussion will be greatly encouraged. Emory medical students as well as experts from Emory School of Medicine and other local universities or organizations will present information. Student volunteers will participate in these sessions by moderating the lectures, assisting with the presentation of information and leading discussions. Participants in this training will be instructed not to change their habitual exercise routines. After completing health education, participants may be assigned to an IG or EG training class but will not undergo evaluations.

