### **Statistical Analysis Plan for Aim 1**

- **Participant characteristics:** Descriptive statistics will describe groups, including disease severity and duration for those with PD. T-tests will compare means (e.g., age, mental status) of participants with and without PD. Data analyses will be completed in SPSS (v. 19).
- **Functional performance measures:** Foot-tapping absolute timing error and average amplitude will be compared between groups with t-tests. These measures will also be correlated to fMRI data.
- **fMRI Brain Activation Analyses:** Following preprocessing and normalization to standard space, activation maps for the IG and EG tasks versus rest will be determined for each subject on a voxel by voxel basis. Regressors of interest will model IG and EG blocks of foot movement for each limb separately. Head motion parameters will be included as additional regressors. A similar approach has been used previously in PD. First level contrast maps (betas) for the IG and EG tasks versus rest derived in each subject will be submitted to a second-level, random-effects analysis with subject as a random factor. Second-level t-maps will be thresholded at  $p <.05$ , corrected for multiple comparisons using the false discovery rate (FDR) method. These activation maps will be used to define circuitry for IG and EG foot-tapping. Average percent signal change for the IG and EG tasks (relative to rest) for each participant will be extracted from the centers of gravity of the activated regions and submitted to hierarchical regression analyses to determine whether they correlate with behavioral measures (absolute timing errors and average amplitude of foot-tapping). Disease severity and duration of illness will be covariates for individuals with PD. **The primary outcome measure will be average percent signal change** for the IG and EG tasks (relative to

rest) to determine and distinguish circuits involved in IG and EG foot-tapping networks in participants with and without PD.

## Power Analyses for Aim 2

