**Hypothesis 1:** Power calculations for Aim 2 are based upon an assumed 4-point improvement and effect sizes  $> 0.8$  on the BBS after 12 weeks of adapted tango, which was attained previously (see Preliminary Studies), and the minimal detectable change on the BBS in parkinsonism is 2.84 points. Therefore, with a total sample size of 63 participants (21 participants in each of 3 groups: IG, EG, and BC) a repeated measures (RM) ANOVA with 3 levels of repeat will be sensitive to between-within interaction main effect size of  $f(v) = 0.44$  ( $F_{4,114} = 2.45$ ) with a power of 0.80 at  $\alpha=.05$ . Post hoc sensitivity to effects between groups will be  $d = 0.90$ , and within groups,  $d_z = 0.65$ . To reflect an anticipated 20% attrition, we will recruit an additional 4 participants per group. Thus we will recruit 25 participants per group, for a total of 75 individuals with PD recruited for Aim 2. **Hypothesis 2:** 25 participants per group will be sufficient to detect effects for the imaging (activation and resting state) components of Aim 2 as well, based on studies conducted to determine reasonable sample sizes for fMRI studies, that demonstrate at least 20 participants in each group are necessary. **Hypothesis 3:** Differences in RSfc have been noted between different groups of individuals with PD in sample sizes of 16 per group; therefore, with 25 individuals per group, we will be able to detect differences between groups.

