## Statistical Analysis Plan for Aim 2, Hypothesis 1, 2 and 3:

- **Participant demographics:** Descriptive statistics will characterize groups. One-way ANOVA will determine differences, if any, between groups on baseline measures.
- **Behavioral Outcome measures:** A 3 group (IG, EG, BC) x 3 time (pre, post test, follow-up (1-month later)) RM ANOVA will be used to detect main effects. Appropriate post hoc tests will be used to determine within- and between-group differences,  $p<0.05$ , for **BBS, the primary outcome** measure upon which Aim 2 is powered. Statistical tests run on all secondary variables will be corrected for multiple comparisons.
- **Brain Activation Analyses for Aim 2, Hypothesis 2:** Similar to Aim 1 procedures, average percent signal change for IG and EG tasks (relative to baseline) for each participant will be extracted from the centers of gravity of the activated regions and submitted to hierarchical regression analyses to determine whether they correlate with behavioral measures (foot-tapping absolute timing errors and average amplitude). Disease severity and PD duration will be covariates. To determine the effects of time and training status we will submit the percent signal change to a 3 group (IG, EG and BC) X 2 time (pre, post) RM ANOVA. Post-hoc analyses will be corrected for multiple comparisons. The **primary outcome** will be t-contrast maps and effect size maps from ANOVA, which will be evaluated for changes in STC and CTC circuits.

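### The primary BBS analysis is a three-visit RM ANOVA with no rule for a missed visit, so a participant who finishes training but misses the 1-month visit drops out of the group x time test despite having pre and post scores

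*Combined protocol and SAP*

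**What the plan says.** The visit schedule in section 5 (Overview) places outcome testing "1 week before training (pre), and 1 week (post) and one month (follow-up) after completing all training". The Aim 2 statistical analysis plan (section 7, behavioural outcomes) applies a 3 group x 3 time model, "pre, post test, follow-up (1-month later)) RM ANOVA will be used", followed by post hoc comparisons whose form is left open. It identifies "BBS, the primary outcome measure upon which Aim 2 is powered".

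The Aim 2 power analysis assumes three repeats per person, "with a total sample size of 63 participants (21 participants in each of 3 groups: IG, EG, and BC"). It then adds a margin: "To reflect an anticipated 20% attrition, we will recruit an additional 4 participants per group", giving 25 per group and 75 in all.

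The only software named for the behavioural statistics appears under Aim 1: "Data analyses will be completed in SPSS (v. 19").

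The Dosage paragraph restricts the analyses to people who finish all 20 lessons. Nothing says what happens to such a person if one test visit is missed: there is no imputation, no mixed model and no intention-to-treat set. The single missing-data statement, in the fMRI preprocessing paragraph, concerns discarded image volumes.

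**The concern.** A classical RM ANOVA, univariate or multivariate, works on a complete vector of visits per person, and the repeated-measures GLM routine in SPSS drops incomplete cases listwise. The 1-month visit falls after classes end. A person can therefore attend every lesson, be tested at post, and still contribute nothing to the primary test because of one later absence.

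This is separate from the 20-lesson rule. It acts on people who satisfy that rule and would remain if the rule were removed.

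Two things are at stake. Observed primary-outcome data are thrown away, which costs power in a design with no slack. Also, membership of the analysis set depends on something that happens after the pre-post effect has been measured. If that later event is related to response, and differently so by arm, the estimate of the immediate training effect could be distorted even though every score needed for it was collected.

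**Working it through.** **1. Reproduce the stated power.** Inputs from the Aim 2 power analysis: N = 63, three groups, three visits, f(V) = 0.44, alpha 0.05, stated power 0.80. I used the noncentral F with df1 = 4, df2 = 2(N - 3) and noncentrality N x f(V)².

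- N = 63: noncentrality 63 x 0.1936 = 12.20, df2 = 120, power 0.792. The stated 0.80 is reproduced to rounding.
- The plan prints 114 denominator df, which corresponds to N = 60, since 2 x (60 - 3) = 114.

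**2. What the attrition margin leaves.** 25 x 0.8 = 20 per group, not 21. N = 60 gives noncentrality 11.62 and power 0.768.

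**3. Listwise loss of lesson-completers who miss only the 1-month visit.** Starting from 20 per group (missed-visit rates are assumed):

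| Miss follow-up only | Per group kept | N | RM ANOVA power | Mixed model power |
|---|---|---|---|---|
| 0% | 20 | 60 | 0.768 | 0.768 |
| 5% | 19 | 57 | 0.743 | 0.763 |
| 10% | 18 | 54 | 0.715 | 0.757 |
| 20% | 16 | 48 | 0.653 | 0.745 |

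The mixed-model column keeps the pre and post scores of those who miss follow-up. It assumes compound symmetry with correlation 0.5 to 0.8 (the figures vary by at most 0.001 across that range), a covariance treated as known, and an effect in one arm that is equal at post and follow-up. If that effect halves by follow-up, power stays at 0.768.

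With 15% lesson non-completion instead (25 x 0.85 = 21.25 per group), RM ANOVA power is 0.798 with no missed follow-ups, 0.746 at 10% missed and 0.685 at 20%.

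**4. Can the pre-post contrast be biased?** I simulated 400,000 people per arm. The true tango-minus-control pre-post effect is 4 points. The SD is 5, which is what the plan's 4 points and an effect size of 0.8 imply (4 / 0.8 = 5). The within-person correlation is 0.5 to 0.85. The log-odds of missing follow-up change by -1 per SD of gain, relative to the arm's own mean, in the arms named. The complete-case effect is then:

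| Who misses follow-up | 10% loss | 20% loss |
|---|---|---|
| Low gainers, tango only (control loss random) | 4.3 to 4.5 | 4.5 to 4.9 |
| Low gainers, control only (tango loss random) | 3.5 to 3.8 | 3.1 to 3.5 |
| Low gainers, equally in both | 4.0 | 4.0 |
| Random in both | 4.0 | 4.0 |

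With half the slope (tango only), the range over 10% to 20% loss is 4.1 to 4.5. With 5% loss at the full slope (tango only), it is 4.1 to 4.2. Using all observed pre and post scores returns 4.0, but by construction, because the simulation removes none of them.

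**The case against.** The strongest reply is that the plan never says anyone will be deleted. That is true: deletion follows from the named method. The post hoc tests are unspecified and could be run on every pre-post pair, so it would go too far to say that such a person loses all their BBS data. Exclusion is certain only for the omnibus test.

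The 20% margin may also have been meant to cover missed visits. Past attrition is given as about 15%, and the last visit comes only about three weeks after the post-test. If missed follow-ups sit inside the margin, or are rare, the cost is small: at 5% missed the comparison is 0.743 against 0.763. A margin protects power, though, and does nothing about selective loss.

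A reader might infer that the treatment effect will be overstated, by 6% to 22% on the tango-only scenario. The documents do not support that. Nothing in them says low gainers skip follow-up, or that only tango participants do. The bias disappears when loss is random or equally gain-dependent, and reverses when it sits in the control arm. An IG versus EG contrast would be free of this bias if both tango arms lose people in the same way.

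A reader might also take the Behavioral Control paragraph, where "participants may be assigned to an IG or EG training class but will not undergo evaluations", as evidence that controls forfeit their 1-month visit. Its natural meaning is that the later tango class is not itself evaluated. Nothing times that class before the follow-up, and the visit schedule exempts no arm. It is not evidence of arm-dependent loss.

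**Conclusion.** The point holds as a limited one. The primary test, as named, discards lesson-completers who lack the 1-month score, and the plan contains no rule that would keep them.

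The loss of usable data is certain for anyone in that position; how many there will be is unknown. If lesson non-completion uses up the 20% margin, power falls from 0.768 to 0.715 or 0.653 at assumed missed-visit rates of 10% or 20%. Keeping the observed scores holds it at about 0.757 or 0.745 under the assumptions above.

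Bias in the pre-post contrast is a possibility, with neither direction nor size established. The scenarios run from about 3.1 to 4.9 around a true 4 points, and those departures need response-related loss that differs by arm. This is a worthwhile, inexpensive improvement to the analysis. It does not show that the planned result would be wrong.

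**What to change.** In the Aim 2 analysis plan, replace the RM ANOVA for BBS with a linear mixed model for repeated measures: group, visit and group x visit as fixed effects, unstructured covariance across the three visits, and every available visit from each participant. Take the pre-to-post and pre-to-follow-up between-group contrasts from that model, so that the post hoc set is also defined. SPSS MIXED does this within the named software.

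The cost is SAP wording only. No new data are needed, and if nobody misses a visit the inference is essentially the same. There are two limits. The model relies on missingness at random given the observed scores, which is weaker than what a complete-case analysis needs but is still an assumption. It also does not bring back participants excluded by the separate 20-lesson rule.

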**Hypothesis 2:** If improved IG foot-tapping performance and mobility (as determined in Aim 2, Hypothesis 1) are related to IG training and planning movement, then we will see IG training-related increased activation in the STC circuit and decreased activation in CTC circuitry. If improved EG foot-tapping performance and mobility are related to EG training and attending to cues, then we will see corresponding increased activation in the CTC circuit.

**Hypothesis 3:** Resting-state functional connectivity patterns will reflect training effects, with connectivity increases primarily in the STC circuit following IG training and in the CTC circuit after EG training; minimal changes will occur following the control intervention.

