- **Brain Connectivity Analyses for Aim 2, Hypothesis 3:** In Aim 2, Hypothesis 3, we will examine RSfc for increases or decreases as a function of training type and evaluate changes for correlations with improvement on behavioral outcomes. We will use regions of interest (ROIs) informed by IG and EG foot-tapping fMRI analyses in Aim 1. Seed ROIs will be 10mm spheres around centers of gravity of clusters of activation in the group level activation maps for IG and EG foot-tapping, in STC areas (posterosuperior putamen, ventral anterolateral thalamus, rostral SMA, and primary motor cortex) and CTC areas (cerebellum Larsell lobules IV, V, and VI, ventral posterolateral thalamus, primary somatosensory cortex, and the ventral premotor cortex). Seed ROIs gained from the foot-tapping task provide one path of inquiry into neural network changes that may occur after training. As RSfcMRI analyses can be extended to other important areas of brain function, we will also use behavioral measures, which may have changed (e.g., spatial

cognition) to determine other ROIs for interrogation of changes in RSfc. For all participants, we will use Pearson's correlation ( $r$ ), to correlate the time series from the seed ROIs with the time series of all other brain voxels. R-maps will undergo Fisher's  $r$  to  $z$  transformation and will be entered into a 2nd level random effects analysis for between group comparison using one way ANOVA in SPM8. T maps will be thresholded at  $p<.005$  ( $Z>2.6$ ). Correction for multiple comparisons will be carried out at cluster level according to random fields theory. Age will be a nuisance covariate in all statistical analysis. To account for head motion-related spurious differences in functional connectivity levels, a nuisance regressor based on the total amount of movement will be included in the design. To determine the effect of time and training status on each group, the  $z$  scores will be submitted to a 3 group (IG, EG, BC) x 2 time (pre, post) RM ANOVA. Post hoc analyses will be corrected for multiple comparisons. The **primary outcomes for Aim 2, Hypothesis 3** will be changes in average connectivity strength across STC and CTC circuits, as measured by average cross correlation coefficient between the seed regions of the circuits.

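### The imaging hypotheses of Aim 2 predict circuit-specific training effects, but the planned ANOVAs are group by time only and no test of circuit specificity is pre-specified.

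*Combined protocol and SAP*

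**What the plan says.** The predictions are in Section 4 (Objectives), Specific Aim 2. Under Hypothesis 2, if the gains come from IG training, "then we will see IG training-related increased activation in the STC circuit and decreased activation in CTC circuitry". If they come from EG training, "then we will see corresponding increased activation in the CTC circuit"; nothing is said there about STC in that arm. Hypothesis 3 predicts resting-state change "with connectivity increases primarily in the STC circuit following IG training and in the CTC circuit after EG training", with minimal change after the control intervention.

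The tests are in Section 7, Statistical Analysis Plan for Aim 2. For activation, the input comes from regions found to be active: "average percent signal change for IG and EG tasks (relative to baseline) for each participant will be extracted from the centers of gravity". The test on these values is then stated as follows: "we will submit the percent signal change to a 3 group (IG, EG and BC) X 2 time (pre, post) RM ANOVA". The primary outcome for that hypothesis "will be t-contrast maps and effect size maps from ANOVA, which will be evaluated for changes in STC and CTC circuits". For connectivity, the z "scores will be submitted to a 3 group (IG, EG, BC) x 2 time (pre, post) RM ANOVA", and the primary outcome is the change in average connectivity strength across the two circuits. Post hoc analyses are to be corrected for multiplicity, but no contrast is named. The plan does not say how several regions and two task signals enter one group by time ANOVA.

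**The concern.** A claim that leading works through one circuit and following through another is a claim about a difference between circuits that itself differs between arms. In ANOVA terms it is a group by time by circuit interaction. The planned models contain group and time only. The other imaging analyses (regressions on tapping performance, a voxelwise group comparison, correlations with behaviour) do not compare circuits either.

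That leaves two readings, both unsatisfactory. If the ANOVA is run once per circuit, the analyst must infer specificity from which circuits reach significance, and that is not a test of the difference. If the signal is pooled over circuits, predicted effects of opposite sign partly cancel.

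What is at stake is the mechanistic conclusion. The Significance section promises to identify the pathways reached by each form of training, and Potential Pitfalls draws therapeutic implications from circuit-specific change.

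**Working it through.** **The plan's own figure.** The only Aim 2 power calculation with an effect size is for the Berg Balance Scale (Hypothesis 1): 63 participants, f(V) = 0.44, F(4,114) = 2.45, power 0.80. With λ = f² × N = 0.44² × 63 = 12.2, the critical F is 2.45 and power is 0.79, so it reproduces under that convention for λ. It says nothing about imaging: no effect size, SD or contrast is given for Hypotheses 2 and 3.

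**Inputs.**
- From Section 7: 25 recruited per arm, 20% attrition, α = 0.05. So 25 × 0.8 = 20 per arm.
- Assumed, because the documents give none: post-minus-pre change with SD 1 in each circuit; between-circuit correlation ρ of 0 to 0.5; effects as stated below; two-sided tests without multiplicity correction.

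**Tests.** For each person let D = STC change − CTC change.
- Planned test per circuit: one-way ANOVA of that circuit's change over three arms.
- Circuit interaction: one-way ANOVA of D over three arms.
- Direct contrast: mean D in IG − mean D in EG, with SE = √[2 × 2(1 − ρ)/n].

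**1. Does group by time separate specific from non-specific effects?** By simulation at 20 per arm, with an effect of 0.9 SD:

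| True pattern | Group × time, STC | Group × time, CTC | Group × time × circuit |
|---|---|---|---|
| Both trainings raise both circuits equally | 0.83 | 0.83 | 0.05 |
| IG raises STC only; EG raises CTC only | 0.83 | 0.83 | 0.95 to 1.00 |

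The planned test rejects equally often in both rows. The interaction tells them apart.

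**2. How often would a specificity claim be wrong?** Take equal true effects, and read IG beating control in STC but not in CTC as specificity.
- Power p for IG versus control in one circuit has noncentrality δ/√(2/20). For δ = 0.9 this is 2.85 and p = 0.79. For δ = 0.6 it is 1.90 and p = 0.45.
- At ρ = 0 the error is about p(1 − p): 0.79 × 0.21 = 0.17 and 0.45 × 0.55 = 0.25. Simulation gives 0.16 and 0.25.
- At ρ = 0.5, simulation gives 0.12 and 0.17.
- With the 21 per arm of the power statement, the range is 0.11 to 0.25.
- The direct contrast errs in the predicted direction in about 0.025.

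**3. What if circuits are pooled?** Assume IG moves STC by +0.65 and CTC by −0.65, and EG moves CTC by +0.65. The pooled IG change is (0.65 − 0.65)/2 = 0, and the pooled EG change is 0.65/2 = 0.325. Power of the pooled group by time test is 0.20 (ρ = 0.5) to 0.29 (ρ = 0). The circuit interaction has 0.98 or more.

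**4. What does the direct contrast cost?** For graded effects (0.9 SD in the trained circuit, 0.45 in the other), the contrast is 0.45 − (−0.45) = 0.9.
- ρ = 0: SE = √(4/20) = 0.447, noncentrality 2.01, power 0.50.
- ρ = 0.5: SE = √(2/20) = 0.316, noncentrality 2.85, power 0.79.

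**5. Is the contrast enough alone?** No. If IG merely lowers CTC by 0.9 SD and nothing else changes, the contrast is again 0.9, and it is significant in the predicted direction in the same 0.50 to 0.79 of trials, with no STC effect and no EG effect.

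**The case against.** A reader might infer that these ANOVAs can never establish specificity. That goes too far. For IG, Hypothesis 2 predicts opposite signs, which two circuit-level tests could show. A crossover of between-arm tests (IG above EG in STC, EG above IG in CTC, both significant) would also show a dissociation. With 20 or 21 per arm its power is about 0.59 to 0.66 under full specificity at 0.9 SD. But these contrasts are not named in the plan, and under graded effects the crossover's power falls to about 0.03 to 0.09. Hypothesis 3, which says the increases are mainly in one circuit, allows graded effects.

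A reader might also infer that the plan leaves the IG-versus-EG comparison to separate within-arm tests. It does not: within a given circuit, group by time compares the arms directly at the 5% level. The gap is between circuits, not between arms.

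The cancellation argument is weaker for Hypothesis 2, because its primary outcome is spatial maps on which STC and CTC stay separate. It applies only if the extracted signal is pooled, which the text neither states nor excludes. The Hypothesis 3 outcome is more ambiguous. Two further limits stand: for EG, Hypothesis 2 predicts only a CTC rise, and a task factor has no meaning for resting-state data.

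Finally, Section 4 describes the mechanistic part of Aim 2 as exploratory, and Aim 2 is powered on the Berg scale. That lowers the stakes. It does not remove them, since directional hypotheses and primary imaging outcomes are stated.

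**Conclusion.** The concern holds in this form: circuit-specific effects are predicted, the imaging ANOVAs contain only group and time, and no test of circuit specificity is pre-specified. The absence is a matter of reading and rests on no assumption.

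Its size does rest on assumptions. With equal true effects of 0.6 to 0.9 SD in both circuits, about 20 per arm and ρ of 0 to 0.5, inferring specificity from the pattern of significance is wrong in about 0.11 to 0.25 of trials, against about 0.025 for the direct contrast. Multiplicity correction would shift these figures, though at ρ = 0 the error p(1 − p) cannot exceed 0.25. The pooled-signal loss (power about 0.2 to 0.3 against 0.98 or more) is conditional on pooling. The plan should be changed, but its design and data collection are not at fault.

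**What to change.** In the Statistical Analysis Plan for Aim 2:
- Add circuit (STC, CTC) as a within-person factor for Hypotheses 2 and 3, and task (IG, EG tapping) for Hypothesis 2 only. State how regions are combined into one value per circuit, and which task signal feeds the main contrast.
- Pre-specify group by time by circuit, with one contrast: (STC change − CTC change) in IG minus the same quantity in EG.
- Pre-specify circuit-level follow-ups, including each training arm against control in its predicted circuit.
- Claim circuit-specific training effects only if the contrast is significant and the follow-ups show the predicted change in the predicted circuit.

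This needs SAP wording only and uses data already planned. The downside is a harder claim. Contrast power is about 0.5 to 0.8 for graded effects, and the joint rule can have no more power than its weakest part: about 0.79 for one arm against control at 0.9 SD with 20 per arm, before any multiplicity correction.
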